10.2 Primary Safety and Tolerability Endpoints

Primary safety endpoints will be the proportion of subjects in the safety population experiencing a TEAE and the proportion of subjects in the safety population discontinuing study drug due to a related AE. Discontinuation from related AE counts will be created by using any discontinuation from related AE documented in the study drug discontinuation page and the AE data for a subject. The first safety endpoint will be evaluated through the Day 28 visit (28 days ± 4 days after randomization). This will be a composite of TEAEs through Day 16 visit and TESAEs through Day 28 visit. The second safety endpoint will be evaluated through the last day of study drug dosing.

For the primary safety end points, the frequency and percentage of subjects with at least one treatment emergent adverse event, and the frequency and percentage of subjects discontinuing study drug due to a related AE, will be determined. Ninety-five percent Clopper-Pearson (exact) confidence intervals will be calculated for each incidence of occurrence by treatment arm. Summaries will be calculated by treatment arm for the overall safety population, by treatment arm stratified within age group, and within age group and formulation for the solithromycin arm. Patient-level information for adverse events and subjects discontinuing study drug due to a related AE will be listed. For this analysis subjects will be grouped according to their randomized treatment arm assignment (intent-to-treat analysis).

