9.6 Blinding

This study will be open-label with a blinded health care professional designated as a subinvestigator at each site. The blinded subinvestigator will be responsible for conducting the clinical outcome (efficacy) assessments.

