12 SAFETY ASSESSMENTS

Safety assessments will include attention to relevant changes in physical examinations, clinical condition, vital signs, and safety laboratory tests that are identified as occurring after the ICF and assent (if applicable) are signed regardless of relationship to study drug. Any study team member may conduct safety assessments.

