12.2 Assessment of Causal Relationship

The investigator must assess the relationship of any AE to the use of study drug, based on available information, using the following guidelines:

- **Unrelated:** There is not a reasonable possibility that the drug caused the event.
- **Related:** There is a reasonable possibility that the drug caused the event; “reasonable possibility” means there is evidence to suggest a causal relationship between the study drug and the AE.

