14 STATISTICAL ASSUMPTIONS

14.1 Statistical Methods and Planned Analyses

14.1.1 Endpoints

The primary endpoints for safety will be:

- The proportion of subjects with TEAEs
- The proportion of subjects with therapy not tolerated. Therapy not tolerated will be defined as discontinuation of drug treatment due to a related AE.

Secondary endpoints include efficacy of solithromycin or active comparator as evidenced by clinical response (see Section 10.7) and population PK of solithromycin.

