3.3 Sample Size and Randomization

Approximately 400 subjects ≥ 2 months to 17 years of age inclusive, with CABP will be enrolled. Subjects will be randomized (3:1) into two groups: solithromycin (N~300) or comparator (N~100). Randomization will be stratified by the following age groups:

- Age Group 1: Adolescents from 12 years to 17 years, inclusive
- Age Group 2: Children from 6 years to <12 years
- Age Group 3: Children from 24 months to <6 years
- Age Group 4: Infants from ≥ 2 months to <24 months

A minimum of 40 subjects will be included in each age group. Approximately 20% of subjects will be enrolled in the United States. Enrollment will occur simultaneously for all age groups for which information to inform the dosing regimen is available.

The sample size of 300 in the solithromycin group is based on the ability to observe an SAE at a frequency higher than 1% (see Table 1).

Table 1 Probability of Observing at Least 1 Subject with a Serious Adverse Event

Number of subjects	Possible Serious Adverse Event Incidence with 5 Days of Dosing				
	0.1%	0.25%	0.5%	1%	2%
100	0.095	0.22	0.39	0.63	0.87
200	0.18	0.39	0.63	0.87	0.98
300	0.26	0.53	0.78	0.95	>0.99

In addition, this sample size will provide reasonable estimates and 95% confidence interval (CI) for safety. If 1 subject has an AE, then the 95% CI (exact binomial) for incidence of that AE within the subject population of 300 subjects is 0.01%, 1.8% (see Table 2).

Table 2 Proportion of Subjects with Adverse Events and 95% CI

Number of events	Proportion	95% CI
0	0	0, 0.012
1	0.003	0.0001, 0.018
2	0.007	0.001, 0.024
3	0.010	0.002, 0.029

The above estimates assume that all 300 subjects assigned to the solithromycin arm will be evaluable for safety and do not account for the possibility that a subject may be excluded from the safety analysis, for example because she/he did not receive any study drug, or withdrew consent prior to completing follow up evaluations for safety.

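### The tolerability endpoint counts only AE discontinuations that unblinded investigators call related; a row for discontinuation due to any AE, with its interval, should stand beside it

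*SAP*

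**What the plan says.** SAP 10.2 defines the second primary safety endpoint as "the proportion of subjects in the safety population discontinuing study drug due to a related AE". Protocol 14.1.1 agrees: "Therapy not tolerated will be defined as discontinuation of drug treatment due to a related AE". SAP 10.2 builds the count from two sources, the study drug discontinuation page and the AE data. It evaluates the endpoint through the last dosing day and gives a Clopper-Pearson 95% interval within each arm. No between-arm test or margin is planned.

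On who decides relatedness, Protocol 12.2 says: "The investigator must assess the relationship of any AE to the use of study drug, based on available information". The answer is related or unrelated, and no blinded or central causality review is described.

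On blinding, Protocol 9.6 says: "This study will be open-label with a blinded health care professional designated as a subinvestigator at each site". It then gives that person's task: "The blinded subinvestigator will be responsible for conducting the clinical outcome (efficacy) assessments". Protocol 12 adds, for safety: "Any study team member may conduct safety assessments".

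Protocol 5.3 gives comparing safety and tolerability with comparators as the reason for the study. SAP section 2 (version 1.1) records termination in March 2018, with fewer than a quarter of the planned 400 enrolled.

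**The concern.** A child who stops drug because of an AE enters the endpoint only if the investigator calls that AE related. The person making that call knows whether the child is on an investigational drug or a familiar antibiotic. That knowledge can push attribution either way, so the filter may act differently in the two arms.

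At stake is the descriptive reading of tolerability. The two proportions and their intervals will be read side by side, because comparison is the study's stated purpose. A gap between them could reflect attribution alone, and equality could conceal a real excess. Discontinuation due to any AE comes from the same records without the causality judgement, so showing it next to the endpoint lets a reader see how much the filter has done.

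**Working it through.** **1. The plan's own figures.** The documents give no figure for this endpoint. The nearest are the sample-size figures in SAP 3.3, which reproduce:
- Probability of at least one SAE at 1% incidence in 300: 1 − 0.99^300 = 0.951 (stated 0.95).
- Exact 95% interval, with lower limit the 2.5% quantile of Beta(x, n−x+1) and upper limit the 97.5% quantile of Beta(x+1, n−x). For 1/300 this gives 0.00008 to 0.0184 (stated 0.0001 to 0.018); for 0/300, 0 to 0.0122 (stated 0 to 0.012).

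The same interval method is used below.

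**2. What existing outputs give.**

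| Output | Content stated | What is not stated |
|---|---|---|
| Tables 14.4.1, 14.4.1.1 | Related-AE discontinuation, exact interval | Any-AE discontinuation |
| Listing 16.2.4.3 | Patients stopping for a related AE | Any-AE discontinuation |
| SAP 7, disposition summary | Timing and reasons for early discontinuation, randomized population | An interval; use of both endpoint sources |
| SAP 9, Table 14.3.1 | Aggregate discontinuation by arm, safety population | A split by reason; an interval |
| SAP 10.3.1, Table 14.4.2 | Counts of subjects with AEs and TEAEs | AEs leading to discontinuation |
| Listings 16.2.2.2, 16.2.7.1 | Early discontinuations; all AEs | Any summary estimate |

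The data should exist. Protocol 12.3 records discontinuation of study drug as an action taken for each AE whatever its causality, and the safety reason in Protocol 11.2 is not limited to related events.

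**3. Model.** Let A be the proportion in an arm who stop for any AE and s the share of those called related. The endpoint is R = A × s. With the same A in both arms, the difference is A × (s1 − s2) and the ratio is s1/s2.

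A and s are assumptions: A from 2% to 10%, s from 30% to 90%. The nearest figure in the documents is adult and covers infusion-site events only. In the Phase 3 IV-to-oral study (Protocol 5.2.4.1), 10 solithromycin and 1 moxifloxacin patients discontinued drug or withdrew. On the denominators in Protocol Table 4 that is 10/434 = 2.3% and 1/429 = 0.2%.

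**4. No true difference (solithromycin versus comparator).**

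| A, both arms | s = 80% vs 40% | s = 40% vs 80% | s = 90% vs 30% |
|---|---|---|---|
| 2% | 1.6% vs 0.8% (+0.8) | 0.8% vs 1.6% (−0.8) | 1.8% vs 0.6% (+1.2) |
| 5% | 4.0% vs 2.0% (+2.0) | 2.0% vs 4.0% (−2.0) | 4.5% vs 1.5% (+3.0) |
| 10% | 8.0% vs 4.0% (+4.0) | 4.0% vs 8.0% (−4.0) | 9.0% vs 3.0% (+6.0) |
| Ratio | 2 | 0.5 | 3 |

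In counts at 300 versus 100 with A = 5%, any AE is 15/300 = 5.0% (2.8 to 8.1%) versus 5/100 = 5.0% (1.6 to 11.3%). With 80% versus 40% called related, the endpoint reads 12/300 = 4.0% (2.1 to 6.9%) versus 2/100 = 2.0% (0.2 to 7.0%).

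**5. A true excess hidden.** Any AE: 30/300 = 10.0% (6.8 to 14.0%) versus 5/100 = 5.0% (1.6 to 11.3%). With 40% versus 80% called related: 12/300 = 4.0% versus 4/100 = 4.0%.

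**6. The size reached.** Fewer than 100 enrolled means at most 99, or about 74 versus 25 at 3:1. One event is 1/74 = 1.4 points on solithromycin and 1/25 = 4.0 points on comparator. For example, any AE at 4/74 = 5.4% (1.5 to 13.3%) versus 1/25 = 4.0% (0.1 to 20.4%) becomes 3/74 = 4.1% (0.8 to 11.4%) versus 0/25 = 0% (0 to 13.7%) if one event per arm is called unrelated.

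**The case against.** The strongest reply has five parts.

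- **Much of the information is already planned.** Disposition gives reasons for stopping, Table 14.3.1 gives aggregate discontinuation in the safety population, and two listings hold the patient detail. This stands as a limit on the point. A reader might infer that any-AE discontinuation is absent from the plan, but the SAP does not support that. Nor does it matter much that disposition uses the randomized population: an undosed child cannot stop a drug, so the counts should match and only the denominators differ slightly. What remains missing is a stated any-AE estimate with an interval, built from the same two sources and set beside the endpoint.
- **The SAP lists table titles, not contents.** Table 14.4.2 may turn out to include AEs leading to discontinuation. That is possible, but SAP 10.3.1 does not say so.
- **The first primary endpoint, any TEAE, has no relatedness filter.** True, but it does not measure treatment-limiting intolerance.
- **The decision to stop is also unblinded.** This stands. Two other arm-specific rules also remain. SAP 3.4 lets an IV-to-oral switch after a related infusion event be recorded as no change in study drug. SAP 9 names an AE as a criterion for premature discontinuation on comparator only. The comparator's variable course partly explains the second rule. But under protocol versions 1.0 to 2.0 an IV solithromycin course stopped for an AE on day 5 or later is not premature by that definition.
- **No between-arm test is planned, and the sample is small.** Both stand. They make this a matter of presentation.

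**Conclusion.** The point holds as a minor one about presentation. A primary endpoint passes through a causality judgement made with knowledge of the arm, and no planned output is stated to show the unfiltered counterpart with an interval.

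Under the assumed rates, 80% versus 40% attribution produces a spurious difference of 0.8 to 4.0 points, and 90% versus 30% produces 1.2 to 6.0 points. Reversed attribution (40% versus 80%) can bring a true 10% versus 5% to equality. These figures rest entirely on the assumed stopping rates and attribution shares.

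Three stronger readings are not supported:
- That attribution was in fact unequal. The documents contain no evidence of this, and neither direction nor size can be known from them.
- That type I error is inflated. With only within-arm intervals planned, the risk is a misleading side-by-side reading.
- That any-AE discontinuation would be free of bias. It removes one filter and leaves the unblinded decision to stop.

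**What to change.** Keep the pre-specified endpoint unchanged. In Table 14.4.1 add one descriptive row, *discontinued study drug due to any AE, regardless of relationship*. Use the safety population, the same discontinuation-page and AE data as SAP 10.2, and a Clopper-Pearson 95% interval per arm. Base tolerability statements in the study report on both rows. State in a footnote that the decision to stop was unblinded and how the IV-to-oral recording rule (SAP 3.4) and the comparator-only AE criterion (SAP 9) bear on the counts, so that those passages are reconciled with the endpoint definition.

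A between-arm difference is not needed, because the plan uses within-arm intervals for these endpoints. The addition fits SAP section 2, which allows extra analyses if they are descriptive.

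The cost is one row from data that should already be collected. Its limit is precision: with zero events the upper limits would be 4.9% for 74 children and 13.7% for 25.

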5.3 Rationale for the Present Study

Although there is evidence of efficacy and safety of solithromycin in adults, the safety and efficacy of solithromycin have not been established in children. There is evidence of similarities in children and adults in 1) CABP definitions and pathophysiology, 2) causative organisms, 3) response to intervention and 4) exposure-response relationship. Therefore, extrapolation of efficacy in pediatric subjects from adult clinical trial efficacy data is reasonable. A safety study in pediatric subjects with CABP, however, is needed to compare the safety and tolerability of solithromycin to comparators. The proposed study will gather necessary safety data and, as a secondary objective, provide an assessment of solithromycin efficacy as CABP treatment in pediatric subjects.

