7.3 Study Drug Dosage and Administration

Solithromycin will be administered IV or PO according to Table 5 through Table 8 below. If dosing begins with oral therapy, the Day 1 dose will be a loading dose. No loading doses are used with IV solithromycin administration or if switched to oral administration. An IV-to-PO switch can occur after the first IV dose. Subjects starting with oral therapy will receive 5 days of solithromycin treatment, and those starting with IV therapy (regardless of if and when they switch to oral therapy), will receive 7 days of solithromycin treatment.

For subjects receiving the capsule formulation, 200 mg solithromycin capsules will be used to provide the absolute dose of either 200 mg, 400 mg, or 800 mg. The capsule dose will be rounded upwards to the nearest 200 mg, not to exceed an 800 mg loading dose and 400 mg maintenance dose. Study drug should be swallowed with water approximately every 24 hours and at approximately the same time each day (± 4 hours). Study drug can be taken without regard to food.

Table 5 Capsule Dosing Regimens

Age (years)	Weight	Route	Formulation	Day 1 (Max dose: 800 mg)	Days 2 to 5 (Max dose: 400 mg)
6 to 17	>30 kg	PO	Capsules	800 mg	400 mg
	>20 to 30 kg	PO	Capsules	600 mg	400 mg
	≤ 20 kg	PO	Capsules	400 mg	200 mg

Subjects requiring an oral dosage form other than capsules will receive suspension formulation, provided at 275 mg/5 mL strengths, to achieve the age-appropriate mg/mL and solithromycin dose. Any dosing variations within 10% of the calculated suspension dose is not considered a deviation.

Table 6 Suspension Dosing Regimens

Age (years)	Route	Formulation	Day 1 (Max dose: 800 mg)	Days 2 to 5 (Max dose: 400 mg)
12 to 17	PO	Suspension	20 mg/kg (800 mg)	10 mg/kg (400 mg)
6 to <12	PO	Suspension	20 mg/kg	10 mg/kg
2 to <6	PO	Suspension	20 mg/kg	10 mg/kg
2 mo to <2	PO	Suspension	20 mg/kg	10 mg/kg

No loading doses are used with IV solithromycin administration. Intravenous solithromycin should be infused over approximately 60 minutes (± 20 minutes) approximately every 24 hours (± 4 hours). Changes to the infusion duration should be discussed with the study medical monitor prior to study drug administration. Any dosing variations within 10% of the calculated IV dose is not considered a deviation.

Table 7 Intravenous Dosing Regimens

Age (years)	Route	Formulation	Days 1 to 7 (Maximum dose: 400 mg)
12 to 17	IV	Solution	8 mg/kg
6 to <12	IV	Solution	8 mg/kg
2 to <6	IV	Solution	8 mg/kg

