Ampicillin	150-200 mg/kg/day intravenously in equally divided doses every 6 hours	-
Azithromycin	10 mg/kg intravenously/orally on day 1 [500 mg maximum dose] followed by 5 mg/kg orally every 24 hours [250 mg maximum dose]	10 mg/kg orally on day 1 [500 mg maximum dose] followed by 5 mg/kg orally every 24 hours [250 mg maximum dose]
Ceftriaxone	50-75 mg/kg/day intravenously in equally divided doses every 12 hours; total daily dose should not exceed 2 g	50-80 mg/kg intravenously once daily
Erythromycin	40 mg/kg/day orally every 6 hours	30-50 mg/kg/day orally every 6 hours
Erythromycin lactobionate	15 to 20 mg/kg/day intravenously in equally divided doses every 6 hours	50 mg/kg/day intravenously/orally in equally divided doses every 6 hours

Note: if doses of comparator drugs noted in the dosing table above differ those prescribed per standard of care, a site can use the locally prescribed dose.

IV-to-PO switch:

Subjects receiving an IV comparator drug (i.e., ceftriaxone, ampicillin) in any age group may be switched to oral treatment using amoxicillin-clavulanic acid PO (amoxicillin component, 45 mg/kg every 12 hours; subjects weighing ≥40 kg, 875 mg every 12 hours or 500 mg every 8 hours) or amoxicillin alone (45 mg/kg every 12 hours, up to a maximum of 4 g/day).

Subjects must receive 5 to 10 days of treatment with comparator. The exact duration of treatment may be determined at the investigator's discretion.

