3.1 Study Design

This is a phase 2/3, randomized, open-label, active control, multi-center study to assess the safety and efficacy of solithromycin in adolescents (12 to 17 years inclusive) and children (≥ 2 months to < 12 years of age) with suspected or confirmed Community-acquired Bacterial Pneumonia (CABP).

Subjects who meet all inclusion/exclusion criteria and sign the informed consent/assent will be enrolled. Subjects will be randomized to receive solithromycin or a comparator antibiotic, administered intravenously (IV) or by mouth (PO) in capsules or suspension formulation, with dosing based on a combination of weight and age. The treatment assignment will be open-label. Subjects will be treated for 5 days with oral solithromycin, 7 days with IV or IV-to-oral solithromycin, or for 5 to 10 days with comparator antibiotics (duration of comparator antibiotic per investigator discretion). Subjects will have daily assessments on days of treatment as detailed in the Protocol, and undergo a follow-up visit on last day of therapy (+48 hours). Subjects will be followed for the occurrence of Adverse Events (AEs) for 16 days (± 4 days) after randomization, and Serious Adverse Event (SAE) monitoring will occur up to 28 days (± 4 days) post randomization. PK samples will be collected to assess solithromycin disposition at specified time points. A blinded clinical signs and symptoms assessment will occur at Screening, and clinical outcomes will be assessed by a blinded health care provider at each site on the Day 3 to 4 visit (early clinical response), the Last Day of Treatment Visit (end-of-treatment response), and at the Day 16 Follow-Up visit (16 ± 4 days post-randomization). If the subject is discharged on Day 2 (prior to the Day 3 to 4 visit), the early clinical response assessment will be done on the day of discharge.

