9 STUDY DRUG ADMINISTRATION

Study drug administration will be summarized in the safety population, by treatment arm, and by treatment arm stratified within consolidated age group. Subjects randomized to solithromycin will also be presented by age group and formulation. Summaries will include a frequency distribution of number of days of drug administration, summary statistics for solithromycin daily dosing amount, and frequency of active comparator antibiotics. Aggregate summaries of treatment discontinuation will be presented. For solithromycin, a subject will be considered to be prematurely discontinued if drug dosing ceases with <5 days on drug for patients starting on PO therapy, and <7 days on drug for patients starting on IV therapy. For active comparator a subject will be considered to be prematurely discontinued if drug dosing ceases with <5 days on drug, or if discontinuation is precipitated by occurrence of an AE. For the purpose of counting days on drug, any date which contains at least a partial dose will be counted. In earlier versions of the protocol (versions 1.0-2.0), 5 to 7 days of solithromycin IV therapy was allowed. For patients enrolled under those protocol versions, premature discontinuation will be determined as <5 days on drug.

For solithromycin subjects, study drug exposure information will be listed, including administered weight-adjusted dose (mg/kg), start and stop date, number of days of dosing, number of days dosing required by protocol which was in effect at the site at the time, loading dose information if applicable, and formulation. For active comparator subjects, details about the active comparator (drug name, dose, dosing frequency), the start date/stop date, and number of days of dosing will be listed.

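### The related-AE discontinuation endpoint is counted over unequal dosing periods (5 or 7 days on solithromycin, 5 to 10 on comparator), so the two arms' proportions mix tolerability with course length

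*SAP*

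**What the plan says.** Protocol 14.1.1 names two primary safety endpoints. For the second it states: "Therapy not tolerated will be defined as discontinuation of drug treatment due to a related AE". SAP 10.2 sets its window: "The second safety endpoint will be evaluated through the last day of study drug dosing". It plans a frequency, a percentage and a Clopper-Pearson 95% interval for each arm. The first endpoint, treatment-emergent events, has the same calendar window in both arms: events through the Day 16 visit and serious events through the Day 28 visit.

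Dosing length differs by arm and by starting route. SAP 3.1: "Subjects will be treated for 5 days with oral solithromycin, 7 days with IV or IV-to-oral solithromycin, or for 5 to 10 days", the last range being for comparator. Protocol 7.3 agrees on solithromycin: "Subjects starting with oral therapy will receive 5 days of solithromycin treatment", with 7 days for those starting IV. For comparator it says "Subjects must receive 5 to 10 days of treatment with comparator" and leaves the exact length to the investigator.

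SAP 9 defines premature discontinuation of solithromycin as "drug dosing ceases with <5 days on drug for patients starting on PO therapy, and <7 days on drug for patients starting on IV therapy". On comparator it is fewer than 5 days, or any stop precipitated by an adverse event. A comparator stop on Day 8 for an adverse event therefore counts.

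Protocol 5.3 says a pediatric safety study "is needed to compare the safety and tolerability of solithromycin to comparators".

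**The concern.** A child who has finished the planned course can no longer discontinue. The endpoint therefore gives each child as many chances to be an event as the planned course allows, and that number depends on arm, route and, for comparator, the investigator's choice. Two regimens with identical day-by-day tolerability can show different proportions on a primary endpoint. The exact intervals do not reveal this, because they express sampling error and not unequal time at risk. SAP 10.2, SAP 10.3 and the table list plan no common-window proportion and no rate per treatment day. Since the study's rationale is a comparison of tolerability, the two proportions will be read side by side.

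**Working it through.** **The plan's own figures.** The documents give no figure for this endpoint. The sample size rests on detecting a serious event in 300 solithromycin subjects: 1 − 0.99^300 = 0.951, against the stated 0.95. The exact interval for 1/300 is 0.0001 to 0.018, as stated. Both reproduce, but neither bears on the window.

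**Step 1: early-stop opportunities.** A stop is early if it comes after the first dosing day or later but before the last planned one, so opportunities = planned days − 1. Course lengths come from Protocol 7.3 and SAP 3.1.

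| Regimen | Planned days | Opportunities |
|---|---|---|
| Solithromycin, oral start | 5 | 4 |
| Solithromycin, IV start | 7 | 6 |
| Comparator | 5 to 10 | 4 to 9 |

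**Step 2: ratios, comparator to solithromycin.**
- 10-day comparator against oral start: 9/4 = 2.25 (10/5 = 2.00 in dosing days).
- 10-day comparator against IV start: 9/6 = 1.50 (10/7 = 1.43).
- 5-day comparator against oral start: 4/4 = 1.00.
- 5-day comparator against IV start: 4/6 = 0.67 (5/7 = 0.71).

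The sign therefore depends on the mix.

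**Step 3: illustration with equal tolerability.** Assume the same constant daily hazard h in both arms; the documents give none. Risk over k opportunities is 1 − (1 − h)^k.

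| k | h = 0.5% | h = 1% |
|---|---|---|
| 4 (oral start; 5-day comparator) | 2.0% | 3.9% |
| 6 (IV start; 7-day comparator) | 3.0% | 5.9% |
| 9 (10-day comparator) | 4.4% | 8.6% |

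**Step 4: a less extreme mix.** Assume comparator durations spread evenly over 5 to 10 days and half of solithromycin subjects starting orally. Mean opportunities are (4+5+6+7+8+9)/6 = 6.5 on comparator and (4+6)/2 = 5 on solithromycin. At h = 0.5% the arm proportions are about 3.2% and 2.5%, a gap of 0.7 points. If all solithromycin subjects start IV, the ratio is 6.5/6 = 1.08.

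**Step 5: hazard that falls with time.** Let the hazard start at 0.5% and be multiplied by q each day. Risk is 1 − ∏(1 − 0.005·q^j) for j = 0 to k − 1.
- q = 0.8: 2.15% at k = 9 and 1.47% at k = 4, ratio 1.46.
- q = 0.5: 0.99% and 0.93%, ratio 1.06.

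Early intolerance shrinks the effect and can nearly remove it.

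**Step 6: precision.** SAP 2 says fewer than one quarter of 400 children were enrolled, so fewer than 100. At 3:1, assume about 25 on comparator. A gap of 0.7 points is then about 0.2 of an event, and 1/25 has an exact interval of 0.1% to 20.4%.

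**The case against.** The strongest reply is that the endpoint is regimen tolerability by definition. A child who completes a 5-day course has tolerated that therapy, and a shorter course is part of what the drug offers. That stands, and is why the planned proportion should be kept.

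Second, the SAP already shows much of what a reader needs. SAP 7 summarises the timing of and reasons for early discontinuation. SAP 9 gives the distribution of days on drug by arm and lists dosing dates. Listing 16.2.4.3 shows each related-event discontinuation. A late event that is new or worsened after dosing also counts in the first primary endpoint, whose calendar window is common to both arms. A reader might infer that better tolerability cannot be told from a shorter window at all. The documents do not support that: individual stops can be inspected. What they do not give is a comparable rate.

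Third, a reader might infer that the endpoint is biased in favour of solithromycin, or that 4.4% against 2.0% is the expected distortion. Neither is supported. Comparator courses may be as short as 5 days and IV-start solithromycin runs 7. The 4.4% and 2.0% pair every comparator child on 10 days with every solithromycin child starting orally, under a constant hazard that the documents do not give.

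Finally, no between-arm test is planned and enrolment was small, so the practical effect is modest. That limits the weight of the point but does not remove it.

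**Conclusion.** The point holds as a limit on interpretation. The planned proportions reflect unequal time at risk, with 4 or 6 early-stop opportunities on solithromycin and 4 to 9 on comparator, and the plan has no like-for-like figure. Depending on the pairing, the ratio of opportunities runs from 0.67 to 2.25. The net size and sign cannot be computed, because route mix and comparator durations are not given. The percentages are illustrations that rest on an assumed hazard common to both arms.

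Two caveats apply to the opportunity counts. Protocol 7 gives 5 to 7 days for both solithromycin routes, whereas Protocol 7.3 gives 5 or 7 by starting route; these passages must be reconciled. SAP 9 also records that protocol versions 1.0 to 2.0 allowed 5 to 7 days of IV therapy, so some IV-start children may have had fewer than 6 opportunities.

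**What to change.** Keep the planned proportion and label it the whole-regimen result. In SAP 10.2 and Table 14.4.1, add the proportion discontinuing for a related adverse event before completing 5 dosing days, counted identically in both arms, with exact 95% intervals. Every regimen then has the same 4 opportunities. Extending the window to Day 10 in both arms would not achieve this, since a completed course cannot be discontinued. Events per 100 treatment days by arm may be added as an option.

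Add a note that the whole-regimen proportions reflect unequal course lengths and that the 5-day row is the like-for-like supplementary figure. It need not be declared the only figure for comparing the drugs, because whole-regimen tolerability is also a fair question.

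The cost is SAP wording and one or two table rows from dosing dates already recorded, with no new data. The downside is that the 5-day row omits later stops, so it has fewer events and wide intervals, especially with fewer than 100 children enrolled. The later stops remain in the whole-regimen row.
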